The primary analysis will assess whether 7 days of treatment is associated with a non-inferior 90-day mortality rate in comparison to 14 days of treatment. We require 1,686 patients per arm to establish a non-inferiority margin of +4% absolute increase in mortality (baseline mortality 22%)⁵ power 80%, alpha 0.025, one-sided equivalence test). We have inflated this to account for a maximum of 5% loss-to-follow-up, and have incorporated early stopping rules to account for the 3 interim analyses (coefficient 1.024)^{6,7} for a total sample size of 3626. Recent landmark trials in with similar baseline mortality rates have used +4% as a non-inferiority margin;^{8,9} the U.S. FDA has recommended a similar margin for analogous industry-sponsored trials.¹⁰ The PneumA study of 8 vs 15 day treatment for VAP used a non-inferiority margin of 10%,¹¹ as have other recent prominent infectious diseases non-inferiority trials,^{12,13} but we believe lower non-inferiority margins are desirable, when feasible, for the outcome of mortality.

5. Statistical analysis

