5.1 Analysis of primary outcome

The BALANCE Trial will be conducted, analyzed and reported according to CONSORT guidelines, including analyzing patients in the groups to which they were assigned (adherent to the intention-to-treat principle).¹⁴ We will also include a per-protocol analysis. Inferences that 7 day treatment is non-inferior to 14 day treatment will be stronger if this finding is confirmed in both intention-to-treat and per protocol analyses.¹⁵ We will also perform a modified intention-to-treat analysis (mITT), excluding patients that die before day 7 of treatment, given that these patients die prior to divergence in treatment assignment.¹⁶ The primary analysis will examine whether 90-day mortality is non-inferior in the 7 vs. 14 day treatment group, as determined by whether the 95.7% confidence interval excludes a 4% absolute increase in mortality. Results will also be reported as relative risks with confidence intervals.

In a secondary adjusted analysis we will use generalized linear mixed models with random effects for center (which was a stratification variable) - with log-link and binomial distribution and report relative risks and confidence intervals. If this model fails to converge we will use modified Poisson regression.¹⁷

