5.4 Frequency of analyses

Three interim analyses occurred for BALANCE, at 1/6 (600 patients), 1/3 (1200 patients) and 2/3 (2400 patients) of total enrollment; we planned to stop at the interim analysis for futility, inferiority or superiority using the O'Brien-Fleming spending function to generate adjusted confidence intervals for the primary endpoint, splitting the type I error at 0.0000007, 0.000452, 0.013, and 0.043 with 99.99%, 99.95%, 98.68% and 95.70% two-sided confidence intervals to give an overall type I error of 2.5%.^{6,7,15} The Data Monitoring Committee (DMC) was guided by a graphical plot indicating mortality differences which would meet futility, inferiority or superiority thresholds. We will perform both frequentist-based and Bayesian-based analyses for the primary outcome at the study's termination. Subgroup analyses were not performed for the interim analyses.

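### The stated boundary levels give an overall one-sided type I error of about 2.4%, not 2.5%, because the O'Brien-Fleming constant for four equally spaced looks was applied to looks at 1/6, 1/3, 2/3 and 1

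*SAP*

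**What the plan says.** Section 4 sets the design error: "power 80%, alpha 0.025, one-sided equivalence test". It adds that the investigators "have incorporated early stopping rules to account for the 3 interim analyses (coefficient 1.024").

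Section 5.4 places the three interim analyses "at 1/6 (600 patients), 1/3 (1200 patients) and 2/3 (2400 patients) of total enrollment", with the final analysis at full enrolment. It derives the boundary "using the O'Brien-Fleming spending function to generate adjusted confidence intervals for the primary endpoint", and gives the result as "splitting the type I error at 0.0000007, 0.000452, 0.013, and 0.043 with 99.99%, 99.95%, 98.68% and 95.70% two-sided confidence intervals". It claims that these levels together hold the overall error at 2.5%.

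Section 5.1 carries the last of these intervals into the primary decision. Non-inferiority depends on "whether the 95.7% confidence interval excludes a 4% absolute increase in mortality".

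**The concern.** An O'Brien-Fleming boundary has a single constant, and its value depends on when the looks occur. The final level of 0.043 is the familiar value for four equally spaced looks, but this trial's looks are not equally spaced. If the constant comes from one schedule and is applied to another, the overall error is no longer the stated 2.5%. The final interval, which is the formal criterion for the primary conclusion, then does not have the error rate that the plan claims for it.

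**Working it through.** **Inputs (SAP).** Overall one-sided error 0.025, coefficient 1.024, baseline mortality 22%, margin 4 points, 1,686 per arm, 5% loss and total 3,626 (section 4). Looks at 1/6, 1/3, 2/3 and the end, with levels 0.0000007, 0.000452, 0.013 and 0.043 (section 5.4). The levels are read as two-sided because the text pairs them with two-sided intervals.

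**Step 1: which boundary is this?** An O'Brien-Fleming boundary has z = C/√t. Convert each level p to z = Φ⁻¹(1 − p/2) and multiply by √t:

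| t | stated level | z | z × √t | level if C = 2.024 | level if C = 2.004 |
|---|---|---|---|---|---|
| 1/6 | 0.0000007 | 4.961 | 2.025 | 0.00000071 | 0.0000009 |
| 1/3 | 0.000452 | 3.508 | 2.025 | 0.000455 | 0.00052 |
| 2/3 | 0.013 | 2.484 | 2.028 | 0.0132 | 0.0141 |
| 1 | 0.043 | 2.024 | 2.024 | 0.0430 | 0.0451 |

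The plan's four figures are reproduced by one constant, C = 2.024.

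**Step 2: which schedule does that constant belong to?** Solve for the C that gives 2.5% one-sided, using the joint normal distribution of the sequential statistics with correlation √(tᵢ/tⱼ):

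- looks at 1/4, 1/2, 3/4, 1: C = 2.0243, final level 0.0429
- looks at 1/6, 1/3, 2/3, 1: C = 2.0040, final level 0.0451 (95.49% interval)

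The coefficient in section 4 points the same way. The inflation factor at 80% power is 1.0238 for four equal looks. For the trial's looks it is 1.017 with C = 2.004 and 1.032 with C = 2.024. The stated total does follow from 1.024: 1,686 × 2 × 1.05 × 1.024 = 3,625.6, or 3,626.

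**Step 3: overall error of the stated levels at the trial's looks.** The one-sided probabilities of first crossing at each look are 0.00000035, 0.000226, 0.006366 and 0.017168. They sum to 0.02376, or 2.38% (4.75% two-sided). A simulation of 10 million paths gives 0.02377. Variants change little:

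- printed confidence levels used as boundaries: 0.02384
- exact C = 2.024: 0.02379
- fractions 600/3,626, 1,200/3,626 and 2,400/3,626: 0.02380

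No standard variant at these looks returns 2.5%. C = 2.024 on equally spaced looks does (0.0250).

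**Step 4: how much wider is the final interval?** Against the constant for the actual looks, 2.0237/2.0040 = 1.0098, about 1%. If the stated interim levels are kept and the remainder of 2.5% is used at the end, the final z is about 1.998 to 1.999 and the level about 0.0455 to 0.0457. That is a 95.43% to 95.45% interval, depending on whether the stated levels, the stated intervals or exact C = 2.024 are used.

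**Step 5: effect on the decision.** Evaluable patients: 3,626 × 0.95 ≈ 3,445, or 1,722.5 per arm. SE = √(0.22 × 0.78 × 2/1,722.5) = 1.412 points.

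- z = 2.0237: half-width 2.857 points; power Φ(4/1.412 − 2.0237) = 79.1%
- z = 1.999: half-width 2.822 points; power 79.8%

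The difference is 0.035 points of half-width against a 4-point margin.

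**Step 6: the descriptions.** The four levels sum to 0.056, so they are nominal levels and not portions of 2.5%. An O'Brien-Fleming-type spending function with one-sided 0.025 at these looks would give 0.00000008, 0.00021, 0.0120 and 0.0463, which are not the listed figures. The listed figures are a fixed C/√t boundary.

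**The case against.** The strongest reply is that the error is in the safe direction and trivial. Type I error is below the claimed 2.5%, and the conclusion could change only if the upper limit fell in a band 0.035 points wide. That stands, and it sets the weight of this point. It does not make the 2.5% statement true.

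A reader might infer that the primary criterion is invalid and that the interval must be narrowed to about 95.44%. The document does not support this:

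- Section 5.4 reports the three interim analyses as already done, so narrowing now would relax the success criterion late, for 0.7 points of power.
- That figure assumes non-inferiority could have been claimed at every look. Section 5.4 names only futility, inferiority and superiority as reasons to stop, and the plot that guided the monitoring committee is not shown. If non-inferiority could be claimed only at the end, the one-sided error is about 1 − Φ(2.0237) = 2.15%, and an ordinary 95% interval would already give 2.5%. The SAP does not settle which reading applies, so 2.15% is conditional.

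A reader might also take the four levels as one-sided. That would give an error of 4.67%, but the text ties them to two-sided intervals.

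The first interval, 99.99%, does not match 0.0000007, which corresponds to 99.99993%. Its neighbours are also printed to two decimals, so truncation is the likely reason. Used literally, it still leaves the overall error at 2.38%.

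It is also fair to say that the levels are fixed in print and that the original O'Brien-Fleming procedure is cited. The spending-function label therefore leaves no doubt about which final interval will be used.

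**Conclusion.** The point holds as a small, conservative arithmetic error. The stated levels give an overall one-sided type I error of 2.38%, not 2.5%, because a constant for equally spaced looks was used on an unequal schedule. The final 95.70% interval is about 1% wider than 2.5% requires. The validity of the primary conclusion is not threatened.

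The 2.38% rests on three assumptions: the looks fell at the planned fractions, the levels are two-sided, and non-inferiority could be claimed at each look. If it could be claimed only at the final look, or if stopping for futility or inferiority was binding, the error is lower still.

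**What to change.** - Keep the 95.70% interval in section 5.1 as the primary criterion.
- In section 5.4, restate the overall one-sided type I error as about 2.4%, and say whether non-inferiority could be claimed at the interim looks, since the error is lower if it could not.
- Describe the four figures as two-sided nominal levels of a fixed O'Brien-Fleming boundary, not as a split from a spending function. Print the first interval as 99.99993% so that it matches its level.
- Only if the sponsor wants exactly 2.5%: recompute the final level before unblinding, from the interim levels and information fractions actually used. On the planned fractions this is about 0.0456 (an interval of about 95.43% to 95.45%), provided non-inferiority could be claimed at every look.

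The first three changes cost a few words and leave the decision rule and the data untouched. The last needs one recalculation and a dated justification.

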5.5 Secondary Bayesian analysis

Usual frequentist-based statistical analysis calculates the probability of obtaining data as extreme or more extreme than the observed data assuming the null hypothesis is true. Interpretations of clinical trials based on frequentist statistics using p-values and 95% confidence intervals can be challenging for clinicians for several reasons. First, frequentist-based analyses usually consider each analysis in isolation, without an easy mechanism for quantitatively incorporating prior information and without a true measure of the probability of clinical benefit. Quantitative interpretation of new information from clinical trials can be especially challenging when either prior evidence or perception does not align with new evidence.¹⁹⁻²¹ The interpretation of results of trials using a non-inferiority perspective can be additionally challenging; requiring interpretation of findings that may indicate non-inferiority, inferiority, superiority, equivalence, or an inconclusive estimate of effect.⁶⁷ Bayesian methods provide an alternative to null hypothesis statistical testing that allow quantification of evidence in favor of the null hypothesis, sequential testing, and comparison of strength of evidence across different studies.⁶⁸⁻⁷¹ In addition to our primary frequentist-based analysis of the primary 90-day mortality outcome we will additionally perform a companion Bayesian analysis. We will combine the data from BALANCE with a non-informative prior to derive the posterior distribution based on which we will report the 95% Credible Intervals together with the probabilities of the difference in mortality between the two groups falling into the superiority, non-inferiority and inferiority region.

References

